This will be a prospective multi-center cohort study comparing changes in sexual function in women undergoing PTNS or MT for OAB/UUI. Potential subjects will be adult women presenting to a urogynecology clinic for symptoms of overactive bladder such as urgency and UUI. Eligible subjects must report urinary urgency or urge incontinence and be recommended for treatment with medical therapy (with anticholinergic or beta agonist) or PTNS by the treating physician. Women meeting inclusion criteria will be asked to complete the validated OAB-q, FSFI, Beck Depression Inventory and a visual analog pain scale prior to therapy and then again after twelve weeks of therapy. Patients will also be specifically asked about the presence or absence of fecal incontinence and known side effects of therapy. Demographic data including age, comorbidities and menopausal status will be extracted from the medical record.

Women meeting inclusion/exclusion criteria will be prospectively enrolled.

- Women who are prescribed MT will be instructed on adherence to therapy for the twelve week duration of the trial. Therapy prescribed (anticholinergic versus beta agonist) will be based on shared decision-making between the patient and the treating physician.
- Women who are prescribed PTNS will undergo weekly 30 minute stimulation sessions for 12 weeks using a tibial nerve stimulator (Urgent® PC, Uroplasty, Minnetonka, MN, USA). The technique consists of stimulating the nerve by means of a 34 gauge needle electrode inserted approximately 2 inches cephalad and 1 inch posterior to the center of the ankle. The needle is inserted at a 60° angle pointing toward the head and advanced until approximately half of the needle is inserted into the leg. The lead wire is then connected to the stimulator and the surface electrode is placed on the inside of the arch of the foot of the treatment leg. The patient treatment level is identified by slowly increasing the current while observing the patient's foot for a motor response (usually toe flex, fan, or twitch) and asking the patient to report any sensations they feel (typically mild pulsing sensation). Once treatment level is identified, therapy mode is initiated and continued for 30 minutes.

Inclusion criteria:

- Female patients greater than 18 years of age

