Sample size calculations were conducted using <http://clincalc.com/stats/samplesize.aspx> with the primary endpoint of FSFI assessed as a continuous variable. Group sample sizes of 63 per group (total 126 patients) will be necessary to detect a clinically relevant difference of 5 points in FSFI assuming standard deviation of 10 [13] and achieve a power of 80%, $\alpha=0.05$. By incorporating a 10% loss to follow-up rate, the investigators propose to recruit 70 patients per group, with a total of 140 patients. Because approximately 45% of patients with OAB will have FSD as determined by an FSFI score below 26.5, the investigators aim to include up to 312 patients in the study.

Initial statistical analysis will provide descriptive statistics on the demographic and clinical characteristics of the study participants using means, standard deviations, median and range for continuous variables and frequencies and percentages for categorical variables. To examine potential differences between the study groups at baseline, descriptive statistics will be obtained for each group and compared statistically using two-sample t-tests, nonparametric rank tests, chi-square and Fisher's exact test as appropriate. All outcome variables will be summarized using similar methods for initial data and 12-week follow-up.

Wilcoxon signed rank test will be used to assess changes in FSFI before and after treatment as the investigators expect the quantitative data from this to have a skewed distribution given the nature of the FSFI score. A subgroup analysis will be performed to determine if those patients with female sexual dysfunction as defined as an overall FSFI score below 26.5 have greater improvements in FSFI than those without. Mann-Whitney U test will be used to compare FSFI scores between the MT and PTNS groups again because of the skewed nature of the distribution. Spearman's correlation will be used to assess for correlation between urinary symptoms, and FSFI.

We will analyze both intention to treat (ITT) and per protocol (treated) samples for the primary outcome. To handle missing data, the investigators will employ multiple imputation models for the ITT analyses. The investigators will also examine the difference between patients who complete the study and those who were

lost to follow-up based on baseline demographic and clinical characteristics to evaluate type of missingness, adherence to therapy and limits to generalizability.

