We will conduct secondary/advanced analyses by specifying multivariate regression models of the primary outcome measures in order to estimate treatment differences adjusted by potential confounders. Specifically, multiple linear regression analyses will be used to adjust the post-treatment change scores for baseline values of the outcome variables as well as age, OAB-q and BMI. These models will be estimated using cluster options (Intercooled Stata, command cluster) to account for the correlations between patients who are treated in the same hospital/site.

A planned interim analysis will be conducted comparing patients receiving anticholinergics and those receiving beta agonists. This will be conducted once 63 patients receiving anticholinergics and 63 receiving beta agonists have completed the study. This will address Aim 3. A Mann-Whitney U test will be used to compare FSFI between patients receiving anticholinergics and beta agonists.

Data Collection and Transmission:

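### The only analysis written for Aim 3 is an unadjusted interim comparison timed to 63 completers in each drug class; the plan neither secures those numbers nor specifies a final Aim 3 analysis

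*Combined protocol and SAP*

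**What the plan says.** All references are to the combined protocol and SAP.

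- **Aim 3** (Specific aims) asks whether changes in sexual function are greater with beta agonists than with anticholinergics.
- **Its analysis** (Statistical analysis and Sample Size Calculation, last paragraph): "A planned interim analysis will be conducted comparing patients receiving anticholinergics and those receiving beta agonists". The timing is "This will be conducted once 63 patients receiving anticholinergics and 63 receiving beta agonists have completed the study", and the paragraph says that this addresses Aim 3. The method is "A Mann-Whitney U test will be used to compare FSFI between patients receiving anticholinergics and beta agonists".
- **Sample size** (same section): 63 per group for MT versus PTNS, for 5 FSFI points at SD 10, 80% power and alpha 0.05. With 10% loss, "the investigators propose to recruit 70 patients per group, with a total of 140 patients". The total is then raised on the ground that only some 45% of women with OAB are expected to score in the dysfunction range of the FSFI, and the new ceiling reads: "the investigators aim to include up to 312 patients in the study".
- **Regression** (same section): models of the primary outcome that "adjust the post-treatment change scores for baseline values of the outcome variables as well as age, OAB-q and BMI", with clustering by site. Drug class is not named.
- **Choice of drug class** (Approach): "Therapy prescribed (anticholinergic versus beta agonist) will be based on shared decision-making between the patient and the treating physician". Potential Difficulties adds that the choice between MT and PTNS is also left to patients and physicians.

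**The concern.** An interim analysis normally precedes a final one. Here the interim analysis is the only one tied to Aim 3, and it waits on a count in each of two classes that nobody controls. The section has no class quota, no end-of-accrual rule and no fallback.

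That leaves two weak outcomes. If the count is reached, the comparison is made at that moment, on part of the MT data, between groups formed by preference, with no adjustment. If it is not reached, the reader cannot tell when Aim 3 is analysed, or whether it is. A count in the smaller class is also a poor guide to information, because an uneven split of a larger MT group can carry more than 63 v 63 and still miss the condition.

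**Working it through.** **1. The plan's own figures.** The normal approximation at 5 points, SD 10, two-sided 0.05 and 80% power gives 63 per group (80.1% power). The plan does not state sidedness; two-sided reproduces its figure. 63/0.9 = 70 per group, 140 in total. 140/0.45 = 311.1, which rounds up to 312. Two Budget lines agree: $6,240/$20 = 312 and $3,120/(100 × $0.10) = 312. So 312 is a costed target, but its stated reason is the prevalence of sexual dysfunction, not the drug-class comparison.

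**2. What the condition needs.** 63 + 63 = 126 MT completers; 126/0.9 = 140 MT recruits. The base plan of 70 MT patients yields 70 × 0.9 = 63 completers in both classes together, so it cannot meet the condition. With 70 PTNS patients the need is 140 + 70 = 210 in total, which is within 312.

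**3. Is it secured?** The documents give neither the MT share of 312 nor the class shares, so both are assumptions here. Two illustrative cases:
- an even split, 156 × 0.9 ≈ 140 MT completers;
- 70 PTNS and the rest MT, (312 − 70) × 0.9 ≈ 218 MT completers.

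The chance that both classes reach 63 is P(63 ≤ X ≤ n − 63), with X binomial(n, p) and p the minority-class share:

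| Minority share | n = 140 | n = 218 |
|---|---|---|
| 50% | 80% | over 99% |
| 45% | 53% | over 99% |
| 40% | 13% | over 99% |
| 35% | 1% | 98% |

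**4. The condition and power.** Information is n1·n2/(n1 + n2). Power is Φ(0.5·√information − 1.96), since 5/10 = 0.5.

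| Completers | Information | Power | Condition met? |
|---|---|---|---|
| 63 v 63 | 31.50 | 80.1% | yes |
| 49 v 91 | 31.85 | 80.6% | no |
| 54 v 164 | 40.62 | 89.0% | no |

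Allowing for Mann-Whitney efficiency of 0.955 with normal scores, these become 78.3%, 78.7% and 87.6%, in the same order.

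**5. If the condition is met and the result stands.** Take 218 MT completers, with completion order unrelated to class. The median number completed when 63 + 63 is reached is the smallest n at which half of the eventual firing probability has accrued. Detectable difference = 2.802 × 10 × √(1/n1 + 1/n2).

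| Minority share | Median n at 63 + 63 | Later completers left out | Detectable then | Detectable at study end |
|---|---|---|---|---|
| 50% | 133 | 85 | 4.9 | 3.8 |
| 45% | 140 | 78 | 4.8 | 3.8 |
| 40% | 157 | 61 | 4.6 | 3.9 |
| 35% | 179 | 39 | 4.4 | 4.0 |

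**6. If all MT completers are analysed at study end.** At 140 completers the detectable difference is 4.7 points (70 v 70) to 5.2 (42 v 98). At 63 completers it is 7.1 (50:50) to 7.7 (30:70).

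**The case against.** The timing sentence says when the comparison is made; it does not forbid one otherwise. The Mann-Whitney sentence carries no condition of its own, so the test and the groups are named whatever the counts. This stands in part. A reader might infer that Aim 3 would have no test if 63 + 63 is missed, and the text does not establish that. What is missing is when, and on whom, the test would then be run. The sentence does sit in the interim paragraph and reads most naturally as that analysis's method.

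Nothing bars an update after the interim look, so the count of omitted completers depends on treating the interim result as final. That also stands, but no update is written, and the paragraph says that the interim analysis addresses Aim 3.

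The planned regression estimates treatment differences in FSFI and could be stretched to drug class. It does not name drug class, so this is ambiguity at best.

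A further tempting inference is that the condition will probably fail. The documents do not support it: the chance runs from 1% to over 99% on shares that they do not give, and 210 patients suitably divided would be enough. Accrual is also reviewed every six months (Data Collection and Transmission), although no action on imbalance is stated. Finally, 49 v 91 against 63 v 63 is a trivial difference in power; 54 v 164 is the more telling example.

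**Conclusion.** The concern holds as a gap in specification. Aim 3 has one written analysis, called interim, unadjusted, and timed to class counts that up to 312 patients can supply but no rule secures. On the natural reading, meeting the condition answers Aim 3 without later completers: roughly 39 to 85 of 218 in the illustrative case, with a detectable difference of 4.4 to 4.9 points where 3.8 to 4.0 was available. Missing it leaves the timing and status of the Aim 3 test undefined even at about 89% power.

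The illustrative figures rest on assumed MT and class shares, the plan's 10% loss, 5 points and SD 10. The wording gap does not depend on them. Nothing here shows that Aim 3 would go untested or that the count is likely to be missed. Minor: one secondary aim, Aim 1 unaffected.

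**What to change.** - **Definitive analysis.** State that Aim 3 is analysed at the end of the study in all MT patients, whatever the class counts.
- **Outcome.** Compare the 12-week change in FSFI between drug classes by Mann-Whitney. The current sentence names FSFI only, whereas Aim 3 concerns changes.
- **Adjustment.** Report beside it the regression already planned, with drug class as the comparison and baseline FSFI, age, OAB-q and BMI as covariates. Other baseline factors already collected, such as menopausal status and depression score, may be added. Residual confounding by drug choice will remain.
- **Site.** Potential Difficulties names five sites. Use a method suited to so few, such as site as a fixed effect, rather than relying on cluster-robust errors alone.
- **The 63.** Keep 63 per class only as the size for 80% power at 5 points and SD 10, and state the detectable difference at the MT number obtained.
- **Early look.** If a comparison at 63 + 63 is kept, label it preliminary. Adding only an end-of-accrual fallback would secure a test but would still omit later completers when the count is reached early.

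The cost is SAP wording; no new data are needed. The downside is a later definitive result, possibly below 80% power if MT numbers are small or uneven: 77% at 42 v 98 and 51% at 31 v 32.

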Identifiers: NCT03500146 Unique Protocol ID: 2016-248

Brief Title: Sexual Function Trial of Overactive Bladder: Medication Versus PTNS (STOMP)

**Document Date 8/22/2017
Uploaded 8/12/2020**

STOMP: Sexual function Trial of Overactive bladder: Medication versus PTNS

Research Plan

Specific aims:

Primary aim:

Aim 1: To determine if there is greater improvement in female sexual function as measured by the female sexual function index (FSFI) with percutaneous tibial nerve stimulation (PTNS) as compared to medical therapy (MT).

Hypothesis: The investigators expect that there will be a greater improvement in overall FSFI with PTNS as compared to MT.

Secondary aims:

Aim 2: To determine if improvement in female sexual function with percutaneous tibial nerve stimulation or medical therapy is correlated with improvement in urinary symptoms as measured by the OAB-q questionnaire.

Hypothesis: The investigators expect that improvement in urinary symptoms will be correlated with improvement in sexual function but that the difference in FSFI between groups will not be solely attributable to differences in urinary symptom improvement.

Aim 3: To determine if changes in sexual function are greater with beta agonist medications as compared to anticholinergic medications.

Hypothesis: The investigators expect that beta agonists will result in improved sexual function as compared to anticholinergics.

Aim 4: To determine if those patients with female sexual dysfunction as defined as an overall FSFI score below 26.5 have greater improvements than those without.

Hypothesis: The investigators expect that patients with female sexual dysfunction will have a greater improvement in FSFI than those without.

Research Strategy

Significance:

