- Symptomatology of urinary urgency or urge incontinence planning to undergo MT or PTNS. Patients must meet a threshold bother defined by a positive response and bother of "somewhat, quite a bit, a great deal, or a very great deal" to questions #2, #3 or #8 on the OAB-q regarding urinary urgency and urgency incontinence.

- Patients may have tried other medication for overactive bladder in the past but should be off therapy for at least one month
- Patients must be currently sexually active with sexual activity within the past month and plans to continue for the duration of the study. Sexual activity, as defined in the FSFI questionnaire, may include caressing, foreplay, masturbation, and vaginal intercourse.
- Patients must be willing and able to complete questionnaires in English

Exclusion criteria:

- Contraindications to PTNS (skin, orthopedic or anatomical limitation that could prevent placement of PTNS electrode, presence of pacemaker)
- Contraindications to both anticholinergic and beta agonist therapy
- Current symptomatic UTI within past week
- Pregnant or planning to become pregnant
- Prior treatment with SNM, PTNS, onabotulinum toxin A or two medications (stopped for reasons unrelated to side effects)
- Diagnosed or suspected interstitial cystitis/painful bladder syndrome
- Diagnosis of neurogenic bladder
- Prolapse greater than Stage 2, pessary use or planned surgery for pelvic floor disorder during the study
- Planned simultaneous treatment with both PTNS and MT

Statistical analysis and Sample Size Calculation:

The proposed study will consist of two treatment groups (MT versus PTNS). The decision to conduct a two-arm prospective cohort as compared to a three-arm randomized controlled trial was based on assessment of feasibility. The primary endpoint of the study is improvement in overall FSFI score which the investigators hypothesize to be greater in the PTNS group.

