Visual analog pain scale		X	X
FSFI		X	X

Follow up medical history			X
---------------------------	--	--	---

Potential Difficulties:

There may be difficulty in recruiting patients for this study as patients may not be sexually active or may think discussion of sexual function is taboo. In order to account for this, the study will be a multi-center trial organized through the American Urogynecological Society-Society of Gynecologic Surgeons Fellows Pelvic Research Network (AUGS-SGS FPRN) to have a greater population from which to recruit patients. This project was submitted and accepted for presentation at the AUGS-SGS FPRN project proposal meeting. The FPRN is a fellow-run multi-center research network created to enable fellows to conduct multi-center pelvic floor research projects. At the meeting, which was held during the annual AUGS meeting on September 28th 2016, multiple sites demonstrated interest and the network decided to undertake the project. All participants within the Fellows Pelvic Research Network are based at academic institutions with sufficient volume to support fellowship training in Female Pelvic Medicine and Reconstructive Surgery. The investigators are currently planning to recruit patients at MedStar Franklin Square Medical Center, Indiana University, Oklahoma University and UT Southwestern Medical Center in addition to MedStar Washington Hospital Center.

There may also be difficulty in adherence to treatment as patients may develop side effects to medical therapy or difficulty in adhering to the weekly schedule for PTNS causing them to stop treatment, these patients will be analyzed with intent to treat analysis. Patients who choose to stop therapy will be asked to fill out completion questionnaires at the time they inform their physician that they would like to stop treatment.

Patients who undergo PTNS often are MT failures thus they may have higher OAB baseline scores and possibly more sexual dysfunction, as patients and their physicians choose treatment in this study, this cannot be controlled for. However, there are many patients in our practice who choose to pursue PTNS as initial treatment as well as patients who choose to pursue MT with a second medication after trying a first. By excluding patients who have failed treatment with two prior medications (stopped unrelated to side effects), the investigators aim to minimize differences between groups.

Budget:

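### Aim 3 compares non-randomised drug classes with an unadjusted test of FSFI; it needs a baseline-adjusted model of FSFI change that includes prior OAB medication

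*Combined protocol and SAP*

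**What the plan says.** The aim (Specific aims, Aim 3) is stated in terms of change: "To determine if changes in sexual function are greater with beta agonist medications as compared to anticholinergic medications".

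Class is not randomised (Approach): "Therapy prescribed (anticholinergic versus beta agonist) will be based on shared decision-making between the patient and the treating physician".

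The eligibility criteria leave three kinds of women in:

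- **One-class contraindication.** The exclusion is "Contraindications to both anticholinergic and beta agonist therapy", so a woman contraindicated to one class only is eligible.
- **One earlier failure.** Inclusion criteria: "Patients may have tried other medication for overactive bladder in the past but should be off therapy for at least one month". The related exclusion is "Prior treatment with SNM, PTNS, onabotulinum toxin A or two medications (stopped for reasons unrelated to side effects"), so one drug stopped for lack of effect does not exclude.
- **Earlier intolerance.** The same exclusion does not count drugs stopped for side effects.

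Potential Difficulties expects such women in the medication group: "patients who choose to pursue MT with a second medication after trying a first".

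The Aim 3 analysis (Statistical analysis and Sample Size Calculation) is triggered when 63 women per class have completed: "A Mann-Whitney U test will be used to compare FSFI between patients receiving anticholinergics and beta agonists". Just before it, the same section describes "multivariate regression models of the primary outcome measures in order to estimate treatment differences adjusted by potential confounders". That model regresses change scores on baseline outcome, age, BMI and OAB-q, with clustering by site. It does not mention drug class.

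**The concern.** Women taking a second drug may differ from women starting their first, both in baseline FSFI and in how FSFI responds. If one class holds more of them, an unadjusted comparison mixes that difference with any class effect. The plan accepts this reasoning for its main contrast: Potential Difficulties says PTNS patients are often medication failures and may have worse bladder scores and more sexual dysfunction. It says nothing similar about the two drug classes.

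The test also leaves the outcome open. A test of 12-week scores and a test of change answer different questions, and a baseline imbalance biases them in opposite directions. The result is meant to help counsel women on the choice of medication, so an artefact of who received which class would matter.

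**Working it through.** **1. The plan's own figure.** Inputs from the sample-size paragraph: difference 5, SD 10, power 80%, alpha 0.05 (two-sided reproduces the figure).

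n per group = 2 × 10² × (1.96 + 0.84)² / 5² = 62.7, rounded up to 63. Power at 63 is 80.1%. Allowing 10% loss, 63 / 0.9 = 70. The arithmetic is sound; the same 63 per class triggers the Aim 3 analysis.

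**2. Bias from a prior-medication imbalance.** Bias b = (difference between classes in the share of second-line women) × (difference in FSFI change between second-line and first-line women). The documents give neither factor, so both are assumed.

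SE = 10 × √(2/63) = 1.78, taking SD 10 for the outcome analysed (the plan does not say whether it is the SD of score or of change). The false-positive rate with no class effect is P(Z > 1.96 − b/1.78) + P(Z < −1.96 − b/1.78), a normal approximation.

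| Imbalance in share | FSFI gap | Bias | False-positive rate |
|---|---|---|---|
| none | any | 0 | 5% |
| 20 percentage points | 3 | 0.6 | 6.3% |
| 20 percentage points | 5 | 1.0 | 8.7% |
| 40 percentage points | 5 | 2.0 | 20.2% |

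Bias can also hide an effect. If the true difference is 5 and the bias is −2, the expected difference is 3; 3/1.78 = 1.68, and power falls from 80% to about 39%.

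**3. Bias from a baseline FSFI imbalance.** With baseline gap g and baseline-to-follow-up correlation ρ, and no class effect, a comparison of 12-week scores is shifted by ρg and a comparison of change by (ρ − 1)g. Simulated false-positive rates (63 per class, normal data, SD 10, 4,000 runs; g and ρ assumed):

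| ρ | g | Mann-Whitney, 12-week score | Mann-Whitney, change | Baseline-adjusted model |
|---|---|---|---|---|
| 0.5 | 2 | 7% | 9% | 5% |
| 0.5 | 3 | 14% | 13% | 5% |
| 0.5 | 5 | 28% | 27% | 5% |
| 0.7 | 2 | 11% | 7% | 5% |
| 0.7 | 3 | 21% | 10% | 5% |
| 0.7 | 5 | 48% | 19% | 5% |

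Subtracting baseline does not cure the bias; adjusting for it does. In these runs baseline FSFI is the only source of imbalance, so the adjusted model is correct by construction. It would not remove the bias in step 2, which needs a prior-medication term.

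**4. What restriction costs.** Suppose 60% of one class and 20% of the other are second-line. Women with no prior drug then number 0.4 × 63 ≈ 25 and 0.8 × 63 ≈ 50. SE = 10 × √(1/25 + 1/50) = 2.45, and power for 5 points is about 53%, before any gain from baseline adjustment.

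**The case against.** - **Change may be what is meant.** Aim 3 speaks of changes, the primary endpoint is improvement, and the plan uses the same shorthand for its PTNS-versus-medication test. This stands. A reader might infer that the plan deliberately tests follow-up scores instead of change; the documents support only an ambiguity to be settled. Settling it in favour of change would not remove the bias (step 3).
- **The adjusted regression may already cover drug class.** Its wording refers only to treatment differences in the primary outcome measures, and FSFI is the primary outcome. But the section defines its treatment groups as medication and PTNS, and Aim 3 then gets its own paragraph and test. Even if extended to class, the model has no prior-medication term.
- **The selection mechanism is inferred.** This stands. A reader might conclude that an earlier failure dictates the class, or that a second drug is of the other class. The documents say only that some women try a second medication. Nor do they link a one-class contraindication to FSFI, so they do not show that such women distort the result.
- **No non-randomised comparison isolates a class effect.** True, and it holds for the proposed model too. The plan chose a cohort for feasibility, and Aim 3 is secondary. That is a reason to label the result associational, but baseline FSFI is already collected and prior medication is easily recorded, so both can be adjusted for.

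**Conclusion.** The point holds. The only analysis assigned to Aim 3 is unadjusted, its outcome is ambiguous, and the comparison is between self-selected groups that may differ in baseline FSFI and prior treatment. The size and direction of any bias cannot be read from the documents. With assumed imbalances, a bias of 0 to 2 points moves the false-positive rate from 5% to about 20%. The upper end needs a 40-point imbalance in second-line share together with an FSFI gap as large as the plan's whole clinically relevant difference of 5; the mildest non-zero case gives only 6.3%. A serious distortion is therefore possible, not demonstrated. The sample size is not at fault, and Aim 1 is not affected by this point.

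**What to change.** Make the main Aim 3 analysis a regression of 12-week FSFI change on the class prescribed at Day 0. Adjust for baseline FSFI, age, baseline OAB-q, BMI and prior OAB medication (none / stopped for lack of effect / stopped for side effects), with site clustering as the plan already provides. State in advance how a woman with both reasons for stopping is classified. Keep the Mann-Whitney test as supportive and say that it is on change.

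Repeat the model in women with no prior OAB drug, labelled as a low-power sensitivity analysis. Report Aim 3 as associational.

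Two steps are best left out of the main model:

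- **Adjusting for prior class.** If prior class does steer current class, little overlap would remain among second-line women.
- **Excluding women with a one-class contraindication.** The eligibility criteria do not require sites to establish this, so recording may be uneven and the exclusion itself selective.

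The cost is a change of plan wording and one or two case report form fields (prior OAB drug and reason for stopping). Eligibility does not settle the reason for stopping when there was only one earlier drug, so it has to be asked for. The sensitivity analysis may have well under 80% power, about 53% in the scenario above. Eligibility, treatment and the Aim 1 analysis stay as they are.

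### Women who stop treatment stay in the ITT analysis, but their FSFI is taken when they announce stopping and no 12-week FSFI is requested from them

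*Combined protocol and SAP*

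**What the plan says.** All references are to the combined protocol and SAP.

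- **Potential Difficulties** foresees stopping for different reasons by group: "patients may develop side effects to medical therapy or difficulty in adhering to the weekly schedule for PTNS". It keeps these women in the analysis: "causing them to stop treatment, these patients will be analyzed with intent to treat analysis". It then sets the time of their last form: "Patients who choose to stop therapy will be asked to fill out completion questionnaires at the time they inform their physician".
- **Approach** schedules the questionnaires "prior to therapy and then again after twelve weeks of therapy". The **Study Timeline** has one FSFI after baseline, at 12 weeks.
- **Statistical analysis and Sample Size Calculation** refers to the same time point: "All outcome variables will be summarized using similar methods for initial data and 12-week follow-up". It adds "We will analyze both intention to treat (ITT) and per protocol (treated) samples for the primary outcome" and "To handle missing data, the investigators will employ multiple imputation models for the ITT analyses".
- **Data Collection and Transmission** allows completion in clinic, online, by mail or by phone. These are general routes and are not tied to follow-up after stopping.

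No section says that a woman who has stopped is still asked for a 12-week FSFI. None says whether her stop-time score is her ITT outcome, or whether her week-12 value counts as missing and is imputed.

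**The concern.** An ITT label suggests that every woman is assessed at the planned time whatever happened to her treatment. Here a woman who stops at week 3, say, would contribute a week-3 score, while a woman who continues contributes a week-12 score. If the stop-time form is the last one sought, her week-12 score is never collected and cannot be recovered later.

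The plan gives side effects as the reason for stopping medication and the weekly schedule as the reason for stopping PTNS. There is therefore no ground for assuming that the groups stop equally often, or that the gap between stop-time and week-12 scores is the same in both. What is at stake is the primary comparison, the PTNS minus MT difference in FSFI improvement.

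**Working it through.** **The plan's own figure.** Inputs from the sample size section: difference 5, SD 10, power 80%, alpha 0.05 (two-sided assumed). n = 2 × (1.960 + 0.842)² × 10² / 5² = 62.8, so 63 per group; 63 / 0.90 = 70. Both figures reproduce. The 10% allowance is for loss to follow-up; no rate is given for stopping treatment.

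**Shift if the stop-time score replaces week 12.** Let p be the share of a group that stops, and g the mean week-12 score minus the mean stop-time score among women who stop. Each group mean then falls by p × g, so the PTNS minus MT mean difference shifts by

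`p_MT*g_MT - p_PTNS*g_PTNS`

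The documents give neither p nor g. The inputs below are assumptions, not a range or a bound:

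- 20% stopping in both groups, gap 2 in both: 0.20 × 2 − 0.20 × 2 = 0.
- 10% in both, gap 2 in MT and 0 in PTNS: 0.10 × 2 − 0.10 × 0 = 0.2 point.
- 30% in MT and 10% in PTNS, gap 5 in both: 0.30 × 5 − 0.10 × 5 = 1.0 point.

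Swapping the groups reverses the sign. The shift is zero for any rates if the gaps are zero, and it can be non-zero with equal rates if the gaps differ.

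**What such a shift does, only if week-12 status regardless of stopping is the target.** With 63 per group, SE = 10 × √(2/63) = 1.78. Normal-theory power at a true difference of 5 is Φ((5 + shift)/1.78 − 1.96):

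- no shift: 80.1%
- shift −0.2: Φ(4.8/1.78 − 1.96) ≈ 77%; shift +0.2: Φ(5.2/1.78 − 1.96) ≈ 83%
- shift −1.0: 61.2%; shift +1.0: 92.0%

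A simulation of the planned Mann-Whitney test (normal scores, SD 10, 63 per group) gives 77% with no shift, 57% at −1.0 and 89% at +1.0. The plan expects skewed scores, so these figures are indicative only.

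**The case against.** **The plan is less open than it looks.** The forms are called completion questionnaires and come directly after the statement that these women are analysed by ITT. The regression models use post-treatment change scores. The Approach section measures FSFI after twelve weeks of therapy, which a woman who stops early cannot supply. A reader might infer that replacement, an additional week-12 form and imputation are three equally open readings. The documents do not support that: replacement is clearly the likeliest. This part of the objection stands. It does not remove the concern, because replacement is the reading that mixes assessment times under an ITT label.

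**A stop-time score is a legitimate on-treatment outcome.** This also stands. Under that target the shift is part of the quantity being estimated. A reader might go further and infer that the plan inflates the false-positive rate, or that recruiting more women ("the investigators aim to include up to 312 patients in the study") makes this worse. That follows only if week-12 status is the target and a non-zero shift exists. The plan does not settle the first, and no figure in it establishes the second.

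**The larger examples use large gaps.** A 5-point gap equals the whole design difference, and milder inputs are no less supported. In a simulation of the 0.2-point case with no true difference, rejection stays at about 5%.

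**Other analyses give some cover.** Per-protocol analysis, multiple imputation and the comparison of completers with women lost to follow-up, which is meant to look at adherence, are all planned. None decides which score enters ITT, and the per-protocol set is defined only as treated.

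**Conclusion.** The concern holds in a limited form. Followed on its likeliest reading, the plan puts off-schedule scores into an analysis labelled ITT and leaves the week-12 scores of women who stop uncollected. Relative to a week-12 target the size and sign of the effect are unknown and zero is possible; 0.2 and 1.0 point are illustrations on assumed stopping rates and gaps. Relative to an on-treatment target there is no bias, but the plan does not say that this is its target.

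The documents do not support a conclusion that the primary comparison is biased, or biased in a particular direction. What they support is that a better method is available at low cost, and that it must be in place before follow-up ends because the missing scores cannot be collected afterwards.

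**What to change.** Amend Potential Difficulties, and cross-refer from the statistical section, so that:

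1. FSFI and OAB-q are requested 12 weeks from Day 0 from every enrolled woman, whether or not she stopped. Use the routes already in Data Collection and Transmission: clinic or online first, mail if she cannot return, phone if neither works.
2. The stop-time form is kept as an additional dated record.
3. The week-12 score is the ITT outcome. An absent one is missing and enters the planned multiple imputation, with the stop-time score as a predictor.
4. The stop-time score is reported as the outcome in an on-treatment sensitivity analysis.
5. Any OAB treatment used between stopping and week 12 is recorded.

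This changes data collection and analysis only, not treatment. If the sponsor prefers the stop-time score as the main outcome, the plan should say so and call it on-treatment, but the week-12 scores would then still be lost.

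**Cost.** One extra questionnaire set per woman who stops. If 10% to 30% stop (assumed), that is 14 to 42 sets for 140 women and about 31 to 94 for 312. The totals below run from 14 sets to 93.6 (30% of 312), all on paper:

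- Copying, assuming half of the 100 budgeted pages at USD 0.10, so USD 5 per set: USD 70 to 468.
- Postage at USD 1.25: USD 17.50 to 117, against a postage line of USD 125.
- Coordinator time, assuming 15 minutes each at USD 45 per hour: 3.5 to 23.4 hours, USD 157.50 to 1,053, against 50 budgeted hours.
- Total: USD 245 to 1,638. The upper figure is 1,638/14,985 = 11% of the full budget, or 1,638/7,500 = 22% of the funding secured so far. Copying and postage fall to zero for forms completed online.

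The sensitivity analysis needs a little more statistical time, not costed here, against 10 budgeted hours. The other downsides are some non-response at week 12 and week-12 scores that may reflect later OAB treatment.
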